### 6.4 Exclusion Criteria

1. Any other central or peripheral nervous system disease that may interfere with the evaluation of ALS or its progression.
2. Presence of a tracheostomy, or use of permanent assistive ventilation (ventilatory support for 23 hours per day or more).
3. Previous exposure to AT-1501.
4. History of malignancy within the previous 5 years, except for localized non-melanoma skin cancers.
5. Women who are pregnant, expecting to get pregnant or who are breast feeding.
6. Abnormal function of the immune system resulting from:
  - Clinical conditions affecting the immune system (e.g. HIV infection, agammaglobulinemia),
  - Systemic administration of corticosteroids (PO/IV/IM) at a dose equivalent to 20 mg/day of prednisone for more than 14 consecutive days within 90 days prior to screening,

- Administration of anti-neoplastic and/or immunomodulating agents (e.g. TNF  $\alpha$  antagonists or anti-B cell antibodies) or radiotherapy within 1 year prior to screening.
7. Recipient of Stem Cell or Gene Therapy.
  8. Serum AST or ALT value greater than 3 times the ULN.
  9. Serum creatinine value greater than 1.5 times the ULN.
  10. Positive test for Hepatitis B surface antigen, Hepatitis C antibody, or HIV.
  11. History of deep venous thrombosis or pulmonary embolism.
  12. Exposure to any other experimental or investigational agent within 30 days or 5 half-lives; whichever is longer.
  13. History of active substance abuse within the past 2 years;
  14. History of stroke, poorly controlled or significant cardiovascular disease, diabetes or any other acute or chronic medical condition that would unreasonably increase the risks of the study procedures, as determined from an interview with the participant and/or review of medical records.
  15. Any other medical condition such as COVID-19, medication, or pre-planned medical/surgical procedure that, in the opinion of the Investigator, would compromise the safety of patients or the integrity of study results.

## 6.5 Handling of Withdrawals

Participants are free to withdraw their consent to the trial at any time without providing reason(s) for withdrawal and without prejudice to further treatment.

It is important to collect safety data on any participant who withdraws consent from the study before their last scheduled visit (End of Study Visit – Week 15). If early withdrawal occurs the clinical site staff is expected to contact the participant for follow-up by both telephone and mail. A minimum of three attempts at contact should be documented, the last with a certified letter, if necessary.

If early withdrawal of consent occurs, the participant should be asked to return for their next scheduled visit (e.g., next study visit or phone assessment) to complete an end-of-study evaluation (Section 7.5). At a minimum the participant should be questioned over the telephone about any changes in clinical condition since their last visit, the status of any ongoing adverse events. The aim is to record data in the same way as for participants who complete the trial.

Patients who withdraw or are withdrawn prior to receiving at least 4 doses of AT-1501 will be replaced within the same dosing cohort that was not completed (i.e. a patient withdrawn from the 1 mg/kg dosing cohort may be replaced with another individual who will receive 1 mg/kg).

## 6.6 Study Drug Discontinuation

Participants may be discontinued from receiving study drug for any of the following reasons:

- Lack of cooperation with study requirements;

- Intercurrent illness, that in the opinion of the Investigator, would unreasonably increase the risks of the study procedures, or otherwise compromise the safety of the participant or the integrity of study results;
- Participant refuses further treatment with AT-1501;
- Actions taken to control the -spread of COVID-19 (e.g. no access to study drug)
- Active COVID-19 infection
- Participant Withdraws consent to the trial;
- Stopping rules are met;
- At the direction of Anelixis;
- At the direction of the Investigator.

The effects of AT-1501 have not been studied in patients that have been diagnosed with COVID-19. It is unknown whether taking the investigational drug will increase or decrease the risk of getting COVID-19 or the effect it may have on the clinical course of a participant who develops COVID-19. Potential participants for the study will be tested for COVID-19 prior to entering the study. If a participant tests positive they will not be allowed to participate in the study. If a participant is diagnosed with COVID-19 while receiving treatment in this study, the administration of the investigational drug will be stopped, and appropriate medical care and follow-up will be done. The participant will continue to be monitored for safety.

All participants that withdraw from treatment with AT-1501 for any reason should continue to be followed until the end of study.

If at any time during the study a participant experiences an adverse event the Investigator believes is severe enough to preclude further AT-1501 administration or the stopping rules are met the participant will be discontinued from study drug treatment and will receive medical treatment as determined by the Investigator. The participant will be followed until the event resolves or until the Investigator determines the AE has reached a stable outcome or is no longer clinically significant. Regardless, each participant will be followed for safety for at least 4 weeks from the last AT-1501 infusion. A final visit will be completed according to the end-of-study evaluation (Section 7.6).

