## 5 INVESTIGATIONAL TRIAL DESIGN

### 5.1 Design

[figure not shown]
This is a Phase 2a, multi-center, open label, multiple dose study of AT-1501, a humanized monoclonal antibody antagonist to CD40LG. Approximately 54 adults with ALS will be enrolled into the study in the United States at up to 12 ALS treatment sites in the United States and 1 site in Canada.

Four ascending doses of AT-1501 (1.0 mg/kg; 2.0 mg/kg, 4.0 mg/kg and 8.0 mg/kg) will be administered as a 1-hour IV infusion to sequentially enrolling cohorts. The 1.0 mg/kg and 2.0 mg/kg cohorts will consist of 9 participants each and the 4.0 mg/kg and 8.0 mg/kg cohorts will consist of 18 participants each. The participants in each cohort will receive 6 bi-weekly (every other week) infusions of AT-1501 over an 11-week period.

The primary objective of the study is to assess safety and tolerability.

[REDACTED]

This study consists of a 4-week screening period, an 11-week dosing period in which participants are dosed once every other week, and a 4 week follow-up period. On Day 1 eligible participants will receive their first 1-hour intravenous (IV) infusion of AT-1501 and will be observed for at least 2 hours post infusion before being released. They will return for clinical visits on Weeks 3, 5, 7, 9 and 11 for subsequent infusions and will remain at the clinical site for at least 2 hours for observation and assessments before being released. Participants will be called weekly between dosing visits (Weeks 2, 4, 6, 8, 10 and 12) by a member of the research team to record adverse events (AE) and changes in concomitant medications. Participants will be followed for an additional 4 weeks after their last dose to monitor for safety, with an end of study clinic visit occurring Week 15.

Each participant will be monitored for safety throughout the study. Safety will be assessed by evaluation of AEs, changes in safety laboratory parameters, physical examination including vital signs, ECGs and the Columbia Suicide Severity Rating Scale (C-SSRS).

The dose limiting toxicity observation period to determine the safety of a dose level is defined as starting with administration of the first dose of AT-1501 to the first participant in a cohort through the administration of the second dose of AT-1501 in the 6th participant in that cohort (See 10.3 for Stopping Rules and Dose Limiting Toxicity).

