#### **6.2 Participant Screening**

The purpose of Screening Visit 1 is to thoroughly inform, both verbally and in writing, the potential participant about the study and allow him/her the opportunity to ask questions. The potential participant will then sign and date the informed consent form and screening procedures can be performed. Once the consent form is signed the participant is considered enrolled into the study and any serious adverse events that occur will be captured from the date of consent until the end of study participation.

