## 7.5 End of Study (Week 15 ± 1 week)

- Symptom directed physical exam (including examination of the injection site and weight)
- Vital signs after 5 minutes in a supine or seated position (blood pressure, heart rate, temperature, respiration rate)
- Blood and urine sample for serum chemistry, CBC with differential and platelet count, coagulation tests, and urinalysis

█ [REDACTED]

- ECG

█ [REDACTED]

- Administration of C-SSRS
- Record concomitant medications
- AE assessment

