#### **10.1.1 Reporting of Adverse Events**

During the study, the Investigator or clinical site personnel will be responsible for querying and recording adverse events and serious adverse events. Events may be spontaneously reported by the participant, discovered during general questioning by the Investigator, or detected through physical examination, laboratory test or other means. Serious adverse events will be collected from the time of informed consent; all adverse events will be collected from the first administration of investigational product until completion of the final visit and will be evaluated by the Investigator/designee for duration, severity, seriousness, and relationship to investigational product, as outlined below. In addition, the actions taken for the AE will also be documented on the eCRF. Full laboratory data are to be collected in this study, and toxicity trends will be analyzed utilizing objective toxicity criteria.

A baseline recording of any symptoms of illness will be performed before administration of the investigational product. Only symptoms that increase in severity or frequency after investigational product administration or new symptoms of illness will be recorded as AEs. If the event reflects worsening symptoms, then this should be captured in the event term. Untoward medical events which occur after signature of the informed consent but before investigational product administration will be recorded as medical history.

For AEs occurring at the site of infusion the phrase “injection-site” or similar should be included in the event term (e.g. treatment-site erythema). AEs will be evaluated using the Common Terminology Criteria for Adverse Events (CTCAE Version 4.03). All AEs will receive a CTCAE categorization from the Investigator. AEs will also be categorized according to relatedness to the investigational product (see Section 0).

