The investigators are responsible for monitoring the safety of patients who have entered this study and for reporting to the Sponsor if serious adverse events (SAE) occur. The Investigator is further responsible for appropriate medical care of patients during the study. The Investigator remains responsible to follow, through an appropriate health care option, AEs that are serious or that caused the patient to discontinue before completing the study. In case of an AE, the patient must be followed until the event resolves or until the Investigator determines the AE has reached a stable outcome or is no longer clinically significant. Frequency of follow-up is left to the discretion of the Investigator. Participant notes throughout the study will be maintained by the Investigator.

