3.2 Schedule of Visits and Assessments

The schedule of visits and assessments is provided in the Appendix.

The planned study week (or day) will be referred to in all tables and listings to enable reviewers to understand the assessment timing without referring to the protocol visit schedule. When assessments/samples are taken at both pre-dose and post-dose on the dosing days, the assessment will be labeled as pre-dose, 2 hours, or 3 hours as scheduled along with the planned study week (or day). Table 2 shows the scheduled study visits, their planned study week, planned study day, and the acceptable visit window from Day 1, for each study visit.

Table 2. Scheduled Study Visits

Scheduled Visit	Planned Study Week	Planned Study Day	Visit Window
Visit 1	Screening	Screening	Day -30 to -1
Visit 2	Week 1	Day 1	-
Visit 3	Week 2	Day 8	+/- 2 Days
Visit 4	Week 3	Day 15	+/- 2 Days
Visit 5	Week 4	Day 22	+/- 2 Days
Visit 6	Week 5	Day 29	+/- 2 Days
Visit 7	Week 6	Day 36	+/- 2 Days
Visit 8	Week 7	Day 43	+/- 2 Days
Visit 9	Week 8	Day 50	+/- 2 Days
Visit 10	Week 9	Day 57	+/- 2 Days
Visit 11	Week 10	Day 64	+/- 2 Days
Visit 12	Week 11	Day 71	+/- 2 Days
Visit 13	Week 12	Day 78	+/- 2 Days
Visit 14 / End of Study	Week 15	Day 101	+/- 7 Days

4. Study Treatments

Four ascending doses of AT-1501 (1.0 mg/kg, 2.0 mg/kg, 4.0 mg/kg, and 8.0 mg/kg) will be administered as a 1-hour IV infusion to sequentially enrolling cohorts. The 1.0 mg/kg and 2.0 mg/kg cohorts will consist of 9 participants each and the 4.0 mg/kg and 8.0 mg/kg cohorts will consist of 18 participants each. The participants in each cohort will receive 6 bi-weekly (every other week) infusions of AT-1501 over an 11-week period.

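### An End of Study visit inside its window can fall as early as 21 days after dose 6, up to 7 days short of the stated 4 weeks of safety follow-up

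*Protocol*

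**What the plan says.** **Length of follow-up.** Protocol 6.6 (Study Drug Discontinuation) says "each participant will be followed for safety for at least 4 weeks from the last AT-1501 infusion". Protocol 5.1 says "Participants will be followed for an additional 4 weeks after their last dose to monitor for safety", with the end-of-study visit at Week 15, and SAP 3.1 repeats this.

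**Visit days.** Protocol Appendix A, SAP Table 2 and the SAP Appendix place the sixth infusion at Day 71 ± 2 and End of Study at Day 101 ± 7. The SAP gives the anchor: "Table 2 shows the scheduled study visits, their planned study week, planned study day, and the acceptable visit window from Day 1". Protocol 7.5 gives only Week 15 ± 1 week, without a day number. Protocol 5.7 puts the time from first dose to the end-of-study visit at no more than 15 weeks.

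**End of adverse event collection.** Protocol 10.1.1: "all adverse events will be collected from the first administration of investigational product until completion of the final visit". The same section keeps open events under observation: "the patient must be followed until the event resolves or until the Investigator determines the AE has reached a stable outcome".

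**Withdrawal of consent.** This has its own rule in Protocol 6.5: "the participant should be asked to return for their next scheduled visit (e.g., next study visit or phone assessment) to complete an end-of-study evaluation".

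**The concern.** The follow-up promise runs from the last infusion, while the visit window runs from the first. Because dose 6 and the final visit each have their own tolerance around Day 1, a late dose 6 and an early final visit shorten the interval between them. The row for the final visit does not carry the 4-week minimum from 6.6.

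Adverse event incidence is part of the primary endpoint (Protocol 5.2.1), and collection of new non-serious events ends at the final visit. After dose 6 the only scheduled contacts are the Week 12 call (Day 78 ± 2) and End of Study. An early final visit therefore leaves the rest of the 28 days with no planned contact. SAP Section 9 tabulates visits outside their window as deviations. On the days in Table 2, a visit at 21 to 27 days would not be among them, so that tabulation would not show that follow-up was short.

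**Working it through.** **Inputs**
- Dose 6: Day 71 ± 2, that is Days 69 to 73 (Protocol Appendix A, SAP Table 2).
- End of Study: Day 101 ± 7, that is Days 94 to 108 (same places).
- Stated minimum: 4 weeks = 28 days (Protocol 6.6).

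**Formula.** Gap = End of Study day − dose 6 day.

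**Planned days.** 101 − 71 = 30 days. This reproduces the stated 4 weeks with 2 days to spare.

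**Extremes inside both windows**
- Shortest: 94 − 73 = 21 days. Shortfall 28 − 21 = 7 days, and 7/28 = 25%.
- Longest: 108 − 69 = 39 days.

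**By day of dose 6**

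| Dose 6 day | Shortest gap now (Day 94) | Earliest day that gives 28 days | In-window days that fall short |
|---|---|---|---|
| 69 | 25 | 97 | 3 |
| 70 | 24 | 98 | 4 |
| 71 | 23 | 99 | 5 |
| 72 | 22 | 100 | 6 |
| 73 | 21 | 101 | 7 |

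Even with dose 6 exactly on its planned day, a visit on Day 94 is 5 days short. Of the 5 × 15 = 75 possible day pairs, 3 + 4 + 5 + 6 + 7 = 25 give less than 28 days. This counts combinations and is not a probability.

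**Who is affected.** If dose 5 (Day 57 ± 2, Days 55 to 59) is the last dose and the participant stays in the study, the gap is 94 − 59 = 35 to 108 − 55 = 53 days. The shortfall therefore concerns participants who receive dose 6.

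**With a 28-day minimum added.** The earliest visit moves to Days 97 to 101, as in the table. The range becomes 28 (for example 101 − 73) to 39 days (108 − 69), and the shortfall is 0. Permitted visit days fall from 15 to between 15 − 3 = 12 and 15 − 7 = 8.

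**Upper end of the window.** Fifteen weeks are 105 days, and Day 1 plus 105 days is Day 106. Days 107 and 108 are inside the window but beyond the limit in Protocol 5.7.

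**The case against.** The strongest reply is that nothing is contradicted. The words setting a minimum stand in the section on drug discontinuation, after a sentence on participants whose dosing ends because of an adverse event or a stopping rule. Those who stop before dose 6 and stay in the study have at least 35 days. If the sentence covers everyone, it already counts from the last infusion, and a site can satisfy it by choosing a later day in the window. The statements in 5.1 and SAP 3.1 contain no minimum, and the planned 30 days meets them.

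Much of this stands. It would be wrong to infer that the documents nowhere tie follow-up to the last infusion, because 6.6 does. It would also be wrong to read 5.1 and SAP 3.1 as in conflict with the schedule, since a tolerance around a planned day does not contradict a nominal duration. But 6.6 refers to each participant, the 4 weeks in 5.1 applies to all, and the table that sites work from shows neither as a limit on the visit.

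The loss is also bounded. The End of Study blood draw takes place on whichever day is used. The Week 12 call covers roughly the first week after dose 6, and open events are followed to resolution or stability. Protocol 10.2.1 excludes serious events only when they occur more than 4 weeks after the last dose, and even then not if the investigator suspects the product or a study procedure. What remains is new, non-serious events starting after an early visit and before day 28. The analyses are descriptive, and no stated summary uses a fixed 28-day post-dose period.

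**Conclusion.** The point holds in a limited form. The planned days are sound. The window permits a final visit 21 to 27 days after dose 6 that counts as in window, although 6.6 states at least 4 weeks. The largest shortfall is 7 of 28 days (25%), it concerns participants who receive dose 6, and its effect is minor. A correction is worth making because it costs almost nothing and protects a safety commitment the protocol itself makes.

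This rests on 4 weeks meaning 28 days, on dose 6 being given inside its own window, and on Day 101 being the planned day. A reader might count Week 15 from Day 99, by the numbering of the dosing weeks, and obtain 19 to 37 days. The documents do not support relying on that: Protocol Section 7 refers to Appendix A, which states Day 101. Nor does the count of 25 in 75 day pairs mean that a third of participants would be short; how often early visits would occur cannot be derived.

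**What to change.** Keep Day 101 ± 7. In Protocol 7.5, Appendix A, SAP Table 2 and the SAP Appendix, add: *and no earlier than 28 days after the actual last infusion, except for participants who withdraw consent and are evaluated under Section 6.5*. Name Day 101 in 7.5 at the same time.

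In Protocol 5.7, replace the 15-week limit with one that matches the window. Day 108 is 107 days after Day 1, or 15 weeks and 2 days.

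The cost is one clause in four places and one edit in 5.7. Sites lose between 3 and 7 of the 15 permitted days, all on the early side, depending on when dose 6 was given. No analysis changes.

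Narrowing the window to Day 101 −0/+7 is not needed. It would also remove the shortfall, but it would put visits on Days 97 to 100 that do give 28 days out of window.

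A separate and optional alignment concerns serious events. Protocol 6.2 says "any serious adverse events that occur will be captured from the date of consent until the end of study participation" and SAP 13.1 stops at the final visit, while Protocol 10.2.1 works with 4 weeks after the last dose. Collecting them to the later of the final visit and 4 weeks after the last dose would reconcile the three.

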## **7 STUDY PROCEDURES**

The assessments to be performed during the study are outlined below. The first day the participant receives AT-1501 is considered “Day 1”. Refer to Appendix A Time and Events Schedule.

### **7.1 Screening (Week -4 to Week -1)**

The Screening Visit is performed to inform the patient about the study and check eligibility for participation. No treatment or study related procedures will be initiated before written informed consent has been obtained. Results from the screening visit and procedures conducted as part of routine standard of care are used to determine study eligibility.

- Record medical history and demographics
- Record concomitant medications
- Complete physical exam including weight and height
- Vital signs after 5 minutes in a supine or seated position (blood pressure, heart rate, temperature, respiration rate)
- ECG
- Blood samples for serum chemistry, CBC with differential and platelet count, coagulation tests, Serum pregnancy test (women of child-bearing potential), Hepatitis B surface antigen, Hepatitis C antibody, and HIV
- COVID-19 testing to be done no later than 1 week prior to the first infusion.
- Urinalysis
- [REDACTED]
- Administration of the ALSFRS-R
- Slow Vital Capacity (SVC), if available
- Administration of the Columbia Suicide Severity Rating Scale (C-SSRS)

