## 8 PROCEDURES AND EVALUATIONS

### 8.1 Assessments of Safety

#### 8.1.1 Medical History and Physical Examination

A medical history is obtained through review of the participant's medical records and personal interview in order to assess eligibility. Assessment of eligibility should include a full review of all concomitant medications and relevant vaccinations or immunizations.

A complete physical examination is performed at the screening visit as well as a COVID-19 test to be conducted no later than a week prior to the first infusion. The complete physical examination will include measurement of height, weight and vital signs. A symptom-directed physical examination (including examination of the injection site and weight) and vital signs is performed pre-dose on the days of dosing. Vital signs include heart rate, respiratory rate, blood pressure (after being seated/supine for at least 5 minutes) and temperature.

A weight change of 10% or greater from the previous measurement will warrant a recalculation of the AT-1501 dose.

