- 13 AT-1501 to be infused over 1 hour using an IV pump. Assessments performed post-infusion are timed from the end of the 1-hour infusion, not the IV-line flush.
- 14 A COVID-19 test will be conducted at screening via nasal swab no longer than 1 week prior to their infusion. If a patient arrives at the treatment center and is symptomatic for COVID-19 subsequent testing may be administered to determine continued study eligibility.

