- 14 A COVID-19 test will be conducted at Screening via nasal swab no longer than 1 week prior to their infusion. If a subject arrives at the treatment center and is symptomatic for COVID-19 subsequent testing may be administered to determine continued study eligibility.

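### The COVID-19 entry test is timed in opposite directions: Protocol 7.1 and 8.1.1 set a latest date of Day -7, footnote 14 of the schedule sets an earliest date of Day -7, and only Day -7 meets both

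*Protocol*

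**What the plan says.** Four places give a time limit for the COVID-19 test at entry.

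- Protocol 7.1 (Screening): "COVID-19 testing to be done no later than 1 week prior to the first infusion".
- Protocol 8.1.1 (Medical History and Physical Examination): "COVID-19 test to be conducted no later than a week prior to the first infusion".
- Protocol Appendix A, footnote 14: "A COVID-19 test will be conducted at screening via nasal swab no longer than 1 week prior to their infusion".
- SAP Appendix, footnote 14: "A COVID-19 test will be conducted at Screening via nasal swab no longer than 1 week prior to their infusion". This copies the protocol schedule and is not an independent second source.

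Protocol 6.6 gives the test its purpose: "If a participant tests positive they will not be allowed to participate in the study". That section also says it is unknown whether the drug alters the risk or the course of COVID-19. It gives no time window.

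The opening of Protocol section 7 sends the reader to the schedule ("Refer to Appendix A Time and Events Schedule"), so a site working from section 7 is given both rules. No other text in either document reconciles them.

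**The concern.** *No later than* one week before sets a deadline: the swab must be done by Day -7. *No longer than* one week before sets a maximum age: the swab must not be done before Day -7. The two phrases limit the same test from opposite sides.

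This is an operative eligibility and safety rule. A site that follows 7.1 and 8.1.1 to the letter may accept a negative result from the start of screening, about four weeks old at the first infusion, and may not use a swab from the last six days before dosing. That defeats the purpose given in 6.6. The two body sections agree with each other, so a reader who checks one against the other gets no hint of a slip.

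There is also a record-keeping consequence. SAP section 9 tabulates protocol deviations, with sub-categories for eligibility, for procedures not done per protocol and for COVID-19. With two opposite rules in force, it is unclear whether a swab on Day -3 or on Day -20 is a deviation.

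**Working it through.** The plan gives no figure of its own to reproduce. The check lists the screening days and applies each rule as written.

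**Inputs**

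- First dose is Day 1 (Protocol section 7). The schedule passes from Day -1 to Day 1 with no Day 0, so Day -d lies d days before the first infusion.
- Screening window: Day -30 to Day -1 (Protocol Appendix A; SAP Table 2), which is 30 days. The heading of Protocol 7.1 gives Week -4 to Week -1, which is 4 × 7 = 28 days. Both are shown.
- Rule A (7.1 and 8.1.1, literal): d ≥ 7.
- Rule B (footnote 14 in both documents): d ≤ 7. The footnote does not say *first* infusion, but it places the test at screening, so it can only mean the first.

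**Counts**

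| | 30-day window | 28-day window |
|---|---|---|
| Rule A, d ≥ 7 | 30 − 7 + 1 = 24 days (Day -30 to -7) | 28 − 7 + 1 = 22 days (Day -28 to -7) |
| Rule B, d ≤ 7 | 7 days (Day -7 to -1) | 7 days (Day -7 to -1) |
| Both, d = 7 | 1 day (Day -7) | 1 day (Day -7) |
| Allowed by B, barred by A | 7 − 1 = 6 days (Day -6 to -1) | 6 days |
| Allowed by A, barred by B | 24 − 1 = 23 days | 22 − 1 = 21 days |
| Oldest acceptable negative, A | 30 days | 28 days |
| Oldest acceptable negative, B | 7 days | 7 days |

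The sets add up: 24 + 7 − 1 = 30 and 22 + 7 − 1 = 28.

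**Sensitivity to day numbering.** If a Day 0 were counted, Day -d would lie d + 1 days before dosing. The single shared day would move to Day -6. The conflict would be the same.

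**Do other provisions close the gap?**

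- Footnote 14 continues: "If a patient arrives at the treatment center and is symptomatic for COVID-19 subsequent testing may be administered to determine continued study eligibility". This is optional and applies only to people with symptoms.
- Exclusion 15 names COVID-19 ("Any other medical condition such as COVID-19, medication, or pre-planned medical/surgical procedure that, in the opinion of the Investigator") but leaves the matter to judgement and requires no test.
- Eligibility is reviewed again before dosing on Day 1, and an examination and temperature are taken then. None of these requires a test of someone without symptoms.
- The COVID-19 row of Appendix A is marked at Screening only, so no Day 1 test is scheduled. That row is the better evidence, because the Day 1 pre-dose list in 7.2 is partly redacted.

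What remains open is the participant who is infected but has no symptoms on Day 1.

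**The case against.** The strongest reply is that this is a slip with one sensible reading. Footnote 14 fits the purpose in 6.6, section 7 points to it, and most sites would probably follow it. A first infusion on a four-week-old result would breach footnote 14, so the protocol taken as a whole does not permit it. A Day -7 swab satisfies both wordings. Day counts are not participants. Even the corrected rule leaves infections acquired after the swab undetected, and no routine test is scheduled before doses 2 to 6. Finally, SAP 7.1 and section 13 base all safety analyses on everyone who received at least one dose, so test timing removes nobody from the primary analysis.

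Most of this stands. The intent can be recovered, the analysis is untouched, and the fix narrows the gap without closing it.

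It does not remove the conflict. The same argument works in reverse: a swab on Day -3, which footnote 14 allows, breaches 7.1 and 8.1.1. On every screening day but one, a site that meets one rule breaks the other. A safety rule at entry should not depend on the site guessing which of two texts was meant.

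**Conclusion.** The inconsistency is real and should be corrected. Protocol 7.1 and 8.1.1 carry the error, and footnote 14 is the intended rule. Read literally, the two rules share 1 screening day out of 30 (or out of 28). The body text accepts a negative result 28 to 30 days old where the footnote accepts 7, and it bars the six days nearest to dosing.

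This rests on reading *no later than* in its ordinary sense and on the schedule having no Day 0. Only the position of the shared day depends on the second point.

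The practical exposure is limited to participants without symptoms on Day 1. The documents give no way to estimate how many would be affected. There is no effect on sample size, error rates or the primary safety counts. The consequences are for safety at entry and for how deviations are classified.

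**What to change.** In Protocol 7.1 and 8.1.1, replace the timing phrase with: *within the 7 days before the first infusion (Day -7 to Day -1)*. All four statements then give the same window.

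Footnote 14 can stay as it is in both documents. Adding the word *first* before *infusion* there would be an optional tidy-up.

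The cost is two phrases in the protocol and no change to the SAP. A participant whose screening visit falls before Day -7 will need the swab nearer to dosing, which footnote 14 already requires.
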